16.1 Confidentiality Policy

The investigator and all personnel involved in the trial will maintain a policy of confidentiality.

16.2 Source Documentation and Case Report Forms

Data will be recorded at sites using CRFs and reviewed during monitoring visits. The recorded data in the EDC system will be verified with source documents. All corrections or changes made to any study data will be appropriately tracked in an audit trail in the EDC system. CRFs will be considered complete when all missing, incorrect, and/or inconsistent data has been accounted for. Data collected at screening will be reported in CRFs, regardless of screening outcome.

Source data (e.g. clinical laboratory reports, ECG printouts) should bear the study number, subject number, date of data generation, and, if reviewed, dated signature of the investigator or designee. Adverse events, concomitant medication data and clinical observations will be in the subjects' hospital notes, or recorded on source data forms, and will be transferred into the CRF after assessment by the investigator or designee.

Other data of medical measurement without print-outs (date and time of study activities, i.e. time of blood sampling, administration of study medication) performed during the study will be captured on the respective laboratory requisition forms or dispensing/administration log, which will serve as source documentation for the respective activities. Data produced by automatic devices with original print-outs (e.g. clinical laboratory test results, ECG traces, blood pressure measurements) will be included in the source documentation. Clinical laboratory parameters will be provided in laboratory print-outs which are to be reviewed, signed and dated by the investigator or designee. Any results outside the normal range should be assessed for clinical significance. The investigator will maintain complete and accurate study documentation in the Investigator Site File.

The investigator will comply with the procedures for data recording and reporting. Any corrections to source documentation must be performed as follows: 1) the first entry will be crossed out entirely, remaining legible; 2) if not self-evident a reason for the change must be given; and 3) each correction must be dated and initialed by the person correcting the entry; the use of correction fluid and erasing are prohibited.

16.2.1 Case Report Forms

The investigator is responsible for the procurement and the quality of source data.

Authorized study site personnel will transcribe source data and source data changes to the CRF. All data should preferably be entered into the CRF on the day of the study visit, but no later than 2 working days thereafter. Changes to a CRF, if not self-evident, will require documentation of the reason for each change. After completion of the study, an electronic (or if necessary paper) version of the complete

set of CRFs for each subject will remain in the investigator file at the study site in accordance with the data retention policy (see Section 16.3).

The handling of data by the Sponsor, including data quality assurance, will comply with regulatory guidelines (e.g. ICH GCP). All data management activities will be conducted by the Sponsor's representative who will follow their SOPs. Data management and control processes specific to the study will be described in the Data Management Plan.

Once all the Data Quality Control steps have been performed, the database will be locked and the records will be released for reporting and statistical analysis. Data will be transferred to the study sites via CDs and transferred to the study Sponsor via an external hard drive. The media will contain subject PDF files of the electronic CRFs.

16.2.2 Computer Systems

Data will be processed using a validated computer system conforming to regulatory requirements.

16.2.3 Data Entry

Data must be recorded using the EDC system. All study site personnel must log into the system using their secure user name and password in order to enter, review, or correct study data. These procedures must comply with the Title 21 Code of Federal Regulations (21 CFR Part 11), Directive 95/46/EC of the European Parliament and of the Council of 24 October 1995 and Directive 2001/20/EC of the European Parliament and of the Council of 4 April 2001. All passwords will be strictly confidential.

16.2.4 Medical Information Coding

For medical information, the following thesauri will be used:

- Latest version of MedDRA for medical history and AEs.
- WHO drug information for concomitant medications.

16.3 Document and Data Retention

The investigator will retain study documentation and data (paper and/or electronic forms) in accordance with applicable regulatory requirements and the data retention policy, as described in the Clinical Study Agreement.

The medical files of study subjects must be retained in accordance with local legislation and in accordance with the maximum period of time permitted by the hospital, institution or private practice.

16.3.1 Data Base Lock

The data base will be locked after all data of the first treatment cycle and of the open label extension phase are entered into the CRF, the data base is confirmed as ‘clean’, and the data review meeting has taken place. Further details will be described in the Data Management Plan.

17. FINANCING AND INSURANCE

The investigator will comply with investigator financing, investigator/Sponsor insurance, and subject compensation policies, if applicable, as described in the Clinical Study Agreement.

18. PUBLICATION POLICY

The investigator will comply with the publication policy as described in the Clinical Study Agreement.

19. REVISION HISTORY

Version	Date	Reason for Revision
1.2	11.03.2016	Clarification on AE follow-up
1.1	28.01.2016	Update in sections 2, 6, 7, 11, 12 and 19, as per BfArM request and FDA advice to address safety procedures and assessments, statistical analyses in the study, minor change in scales, and contact details for reporting SAEs and AESIs
Final version	13.10.2015	N/A (original document)

20. SUPPLEMENTS

[figure not shown]
20.1 Glabellar Line Scale - Subject (GLS-S)

- Glabellar lines, also known as frown lines, are the vertical wrinkles between your eyebrows that may appear worse when you frown.
- In this questionnaire you will be asked to rate the severity of your glabellar lines (how deep they are) when your face is relaxed (at rest) and then when you are frowning.
- Please use the accompanying drawings and the photo atlas to help you make your ratings.
- Not everyone's lines are the same on both sides of their face. Please use your most severe line to score the questionnaire.

1) Line severity at rest

[figure not shown]
- Please look directly in a mirror in a well-lit room with nothing obstructing your face (for example, tie back your hair or use a hairband, remove any make up and ensure your glasses do not obstruct the area between your eyebrows) and rate the lines between your eyebrows as they appear **when your face is relaxed** (at rest).
- Check the most appropriate scale score in the table below:

[figure not shown]

2) Line severity when frowning

- **Now please frown** (push your eyebrows together as far as they will go, as if you are feeling angry, using your facial muscles not your fingers) and look in the mirror. How would you rate the lines between your eyebrows now?
- Check the most appropriate scale score in the table below:

20.2 Glabellar Line Scale – Investigator (GLS-I)

- In this questionnaire you will be asked to rate the severity of the patient’s glabellar lines when their face is at rest and when they are at maximum frown.
Please use the accompanying drawings and the photo atlas to help you make your ratings.
- If the patient has any asymmetry in their glabellar lines, please use the most severe line to score the questionnaire.

1) Line severity at rest

[figure not shown]
Ask the patient to remove anything obstructing their forehead area (for example glasses and make-up, and tie back their hair or use a headband if necessary). In a well-lit room, and when the patient is looking directly at you, please rate the severity of the patient's glabellar lines **at rest**:

2) Line severity at maximum frown

Please now rate the severity of the patient's glabellar lines **at maximum frown** (asking the patient to push their eyebrows together as far as they will go):

20.3 GL-QoL (Modified Skindex-16)

During the past week how much have your glabellar lines bothered you? Glabellar lines are the vertical lines between your eyebrows that are more noticeable when you frown.

For each question please check the box from 0 (Never bothered) to 4 (Always bothered) that best represents how much the lines between your eyebrows have bothered you. If the question is not relevant to you, please check 'Never bothered'.

20.4 FACE-Q Appraisal of Lines Between Eyebrows Scale

FACE-Q APPRAISAL OF LINES-BETWEEN EYEBROWS

These questions ask about how you look right now. For each question, circle only one answer. With the area between your eyebrows in mind, in the past week, how much have you been bothered by:

20.5 FACE-Q Age Appraisal VASScale⁴⁴

FACE-Q AGE APPRAISAL-VAS

[figure not shown]
We would like to know how old you think you look. How many years younger or older do you think you look compared with your actual age?
Please circle one number below:

20.6 FACE-Q Satisfaction with Outcome Scale⁴⁵

FACE-Q SATISFACTION WITH OUTCOME

We would like to know how you feel about your most recent procedure. For each statement, circle only one answer. Please indicate how much you agree or disagree with each statement.

20.7 Subject BMI Formula and Calculation

Table 20-1 BMI Formula and Calculation	
Measurement Units	BMI Formula and Calculation
Pounds and inches	Formula: weight (kg) / [height (m)] ² Calculate BMI by dividing weight in kilograms (kg) by height in meters (m) squared.

MedDRA	Medical Dictionary for Regulatory Activities
MFAS	Modified Full Analysis Set

Statistical Analysis Plan (SAP)

NCS	Not clinically significant
PRO	Patient reported outcome(s)
PP	Per-protocol analysis set
PT	Preferred term
ROS	Review of systems
SAE	Serious adverse event
SAF	Safety analysis set
SAP	Statistical analysis plan
SD	Standard deviation
SOC	System organ class
SOPs	Standard Operating Procedures
TEAE	Treatment Emergent Adverse Event
TFL	Tables, figures, and listings
US	United States
VAS	Visual Analog Scale

Statistical Analysis Plan (SAP)

1 INTRODUCTION

The purpose of this Statistical Analysis Plan (SAP) is to provide detailed descriptions of the statistical methods, data derivations and data displays for study protocol CPH-301-201030 Version 1.2 “Randomized double blind Phase 3 study to assess the efficacy and safety of BoNT/A-DP in the treatment of glabellar lines in comparison with placebo followed by an open label extension study” dated 11 Mar 2016 for the final analysis. The table of contents and templates for the tables, figures, and listings (TFLs) will be produced in a separate document.

Any deviations from this SAP will be described and justified in the Clinical Study Report (CSR).

The preparation of this SAP has been based on International Conference on Harmonization (ICH) E9 guideline and the Code of Federal Regulations (CFR) 21, part 11.

All data analyses and generation of TFLs will be performed using SAS 9.3® or higher.

2 STUDY OBJECTIVES

2.1 Primary objective

To assess the efficacy of BoNT/A-DP in reducing the severity of glabellar frown lines following treatment (compared with placebo) based on investigator and subject assessment at week four (from the first treatment cycle).

2.2 Secondary objectives

1. To assess the proportion of responders at maximum frown and at rest at various time points after each treatment, based on investigator and subject assessments.
2. To assess onset of effect and the duration of effect (at maximum frown) after a single treatment with BoNT/A-DP compared with placebo (first treatment cycle), based on investigator and subject assessments.
3. To provide long term safety data of BoNT/A-DP based on multiple treatment cycles and to establish a sufficient safety database to support regulatory approval.
4. To assess the psychological impact of BoNT/A-DP treatment on subjects (in terms of emotional and social functioning and concerns relating to their glabellar lines) in comparison with placebo after a single treatment.
5. To assess subject perceptions of effect of, and satisfaction with, treatment in comparison with placebo (first treatment cycle) and during the open-label extension phase.

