4.5.1.2 Justification for Schedule

The study schedule includes a maximum of four permitted treatments per subject (four treatment cycles), separated by a minimum interval of 12 weeks, during the study time frame of up to 60 weeks in treatment phase. A minimum interval of 12 weeks between treatments was selected, since the median duration of effect has been reported to be 85 days (12.1 weeks)³¹ and this treatment interval has been evaluated in several repeat treatment studies^{32,33}.

However, since treatment duration of 120 days³⁴, 17.1 ± 6.5 weeks³⁵ or four to six months³⁶ have been reported and re-treatment intervals have been estimated at a mean of 3.9 months³⁶, the schedule has been devised flexibly such that subjects can obtain re-treatment when they qualify (according to the "Eligibility Criteria for Re-

treatment" Section 7.3), which can be at week 12 at the earliest or at four weekly intervals thereafter. Hence, the duration of effect of BoNT/-DP will be evaluated in the first treatment cycle compared with placebo. The duration of effect of BoNT/-DP after repeat treatment will be assessed in the open label extension study. The duration of effect has been reported to increase with repeat treatment³⁷.

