4.2 Key Secondary efficacy endpoints

The key secondary efficacy endpoints of this study are:

1. The percentage of responders at maximum frown at week 12 (after the first treatment with BoNT/A-DP or placebo).
2. The percentage of responders at week 16 (after the first treatment).
3. The proportion of subjects with a ≥ 1 point reduction in FWS score at rest at week 4 in the first treatment cycle, based separately on the investigators' and the subjects' in-clinic assessments (applicable only for subjects who have a FWS score at rest ≥ 1 at baseline).
4. The percentage of responders at week 20 or later (after the first treatment).
5. The extent of change in psychological impact (emotional and social functioning and concerns relating to their glabellar lines) at week 4 after the first treatment, in the BoNT/A-DP group in comparison with placebo, relative to baseline, as assessed by the modified Skindex-16 (Glabellar Line Quality of Life Scale [GL-QoL]) and the FACE-Q (Appraisal of Lines Between Eyebrows and Age Appraisal visual analog scales (VAS)), respectively.

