8.6.3 Analysis of secondary efficacy endpoint(s)

The following order of tests will be defined for the analysis of the key secondary endpoints:

- Primary endpoint (composite endpoint)
- Key secondary endpoint 1 (composite endpoint)
- Key secondary endpoint 2 (composite endpoint)
- Key secondary endpoint 3
 - 3.1: The investigator's in-clinic assessments
 - 3.2: The subject's in-clinic assessments
- Key secondary endpoint 4 (composite endpoint)

Statistical Analysis Plan (SAP)

- Key secondary endpoint 5
 - 5.1: The modified Skindex-16 (GL-QoL) Emotional domain
 - 5.2: The modified Skindex-16 (GL-QoL) Functioning domain
 - 5.3: The modified Skindex-16 (GL-QoL) Overall score
 - 5.4: The FACE-Q Appraisal of Lines Between Eyebrows scale
 - 5.5: The FACE-Q Age Appraisal VAS score

For key secondary endpoints 2 – 4, the p-value to be considered within the hierarchical testing procedure is the one resulting from the Cochran-Mantel-Haenszel test as described for the primary efficacy endpoint in the first paragraph entitled “Primary Analysis” of section 8.6.2.

Analysis of key secondary endpoint 1: The percentage of responders at maximum frown (as defined above for the primary efficacy endpoint) at week 12 (after the first treatment with BoNT/A-DP or placebo).

The same analyses, inclusive the additional exploratory analyses, as described for the primary endpoint will be conducted.

Analysis of key secondary endpoint 2: The percentage of responders at maximum frown (as defined above for the primary efficacy endpoint) at week 16 (after the first treatment).

The analysis of the week 16 visit will be conducted on observed values only, i.e. missing investigator or the subject in-clinic assessments with the FWS at baseline or week 16 visit will be excluded from analysis but not assigned as being non-responders. Subjects who were re-treated before visit week 16 are considered to be non-responders.

In addition, the same analyses, inclusive the additional exploratory analyses, as described for the primary endpoint will be conducted as exploratory analyses. Subjects who were re-treated before visit week 16 are considered to be non-responders in all these analyses.

Analysis of key secondary endpoint 3: The proportion of subjects with a > 1 point reduction in FWS score at rest at week 4 in the first treatment cycle, based separately on the investigator and the subject in-clinic assessments

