In general, the same statistical analyses, inclusive the additional exploratory analyses as described for the primary endpoint, will be conducted.

The analysis using the investigator’s in-clinic assessment will be conducted first with respect to the hierarchical order of key secondary endpoints, with the analysis using the subject’s in-clinic assessment second.

Statistical Analysis Plan (SAP)

All analyses (inclusive the additional exploratory analyses) on the investigator's in-clinic assessment will be conducted only for subjects who have an investigator's in-clinic assessment of a FWS score at rest > 1 at baseline. This will similarly be applied for the analyses of the subject's in-clinic assessment.

For the primary analysis (to be considered within the hierarchical testing procedure), subjects with missing investigator in-clinic assessments of FWS score at rest at baseline or week 4 visit will be assigned as being non-responders for this endpoint. This will similarly be applied for the subject's in-clinic assessment within the primary analysis.

As a consequence, the primary analysis will lead to exactly the same results as the LOCF analysis and thus the LOCF analysis will be skipped.

Analysis of key secondary endpoint 4: The percentage of responders at maximum frown (as defined above for the primary efficacy endpoint) at week 20 or later (after the first treatment).

The analysis of visit week 20 will be conducted on observed values only, i.e. missing investigator or the subject in-clinic assessments on FWS at baseline or visit week 20 will be excluded from the analysis but not assigned as being non-responders. Subjects who were re-treated before visit week 20 are considered to be non-responders.

In addition, the same analyses, inclusive the additional exploratory analyses as described for the primary endpoint, will be conducted as exploratory analyses (for subgroups also).

Analyses of other visits after first treatment but before re-treatment up to week 48 are exploratory only based on the FAS using descriptive statistics only. Subjects with re-treatment before the respective visit will be excluded from the analysis. Additional exploratory analyses, as described for the primary endpoint, will not be conducted, with the exception of the calculation of 95% CIs.

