8.6.4 Additional secondary analyses

The additional secondary efficacy endpoints will be analyzed applying the appropriate statistical method for the comparison of both treatment arms. For proportions

- of responders with a FWS score of 0 or 1 and an improvement ≥ 2 points in FWS score at maximum frown,
- of subjects with ≥ 2 point reduction in FWS at maximum frown,
- of subjects with a ≥ 1 point reduction in FWS at rest, and
- of subjects with an improvement of ≥ 2 points in FWS at maximum frown at 4 weeks after re-treatment,

the Cochran-Mantel-Haenszel test (with stratification variable site) and the Pearson χ^2 -test will be applied. In case of a total number of observations below 30, or in case of at least one cell frequency below 5, Fisher's exact test will be used instead of the χ^2 -test. Two-sided 95% CIs for response rates will be calculated, where appropriate. Additionally the cumulative proportions of effects at weeks 1, 2, and 4 will be calculated. Time to onset of effect in the first treatment cycle will be analyzed descriptively and by using the Kaplan-Meier method. Moreover, the daily assessments of the line severity when frowning will be analyzed descriptively. The FACE-Q satisfaction with outcome scale will be analyzed descriptively.

All endpoints, with exception of “responder” 4 weeks after re-treatment, will be analyzed for the first treatment cycle only. The analysis of “responder” 4 weeks after re-treatment will be conducted on observed values only, i.e. subjects with missing investigator or the subject in-clinic assessments on FWS week 4 or at the preceding end of the cycle visit will be excluded from analysis. Subjects who were treated with placebo during the first treatment cycle are excluded from the analysis of this endpoint, but not assigned as being non-responders. A two-sided McNemar test (using a significance level of 0.05) will be used to compare the response proportions between week 4 re-treatment visit and at the preceding end of the cycle visit. This endpoint will be separately analyzed for each open label extension cycle.

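### Duration of effect is a stated objective without a time-to-event analysis, and the exploratory tables after week 20 drop re-treated subjects and so overstate late response

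*SAP*

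**What the plan says.** Duration in the first cycle is half of secondary objective 2 (Protocol 5.3; SAP 2.2): "To assess onset of effect and the duration of effect (at maximum frown) after a single treatment with BoNT/A-DP compared with placebo". Protocol 4.5.1.2 repeats the commitment: "the duration of effect of BoNT/-DP will be evaluated in the first treatment cycle compared with placebo". Protocol 6.3.1 gives it as a reason for the flexible schedule.

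No endpoint in SAP 4.1 to 4.3 is a duration. Three parts of the SAP bear on the question:

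- **Weeks 12, 16 and 20 (key secondary endpoints 1, 2 and 4).** These are composite responder rates against placebo, tested in the confirmatory hierarchy. Re-treated subjects stay in as non-responders. For the additional week 16 analyses the SAP says "Subjects who were re-treated before visit week 16 are considered to be non-responders in all these analyses", and for week 20 "Subjects who were re-treated before visit week 20 are considered to be non-responders".
- **Other cycle 1 visits up to week 48 (SAP 8.6.3, under key secondary endpoint 4).** These are exploratory and descriptive, in the FAS, with a different rule: "Subjects with re-treatment before the respective visit will be excluded from the analysis".
- **Time-to-event methods (SAP 8.6.4).** The only one is for onset: "Time to onset of effect in the first treatment cycle will be analyzed descriptively and by using the Kaplan-Meier method".

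**The concern.** A responder rate at a fixed visit is not a duration. It cannot separate subjects who never responded from those who responded and relapsed, and it gives neither a median nor a curve. The responder definition also needs an improvement of at least 2 points. A subject who starts at FWS 2 and holds a score of 1 is therefore a non-responder throughout, although not relapsed by the re-treatment criterion in Protocol 7.3.

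The exploratory tables after week 20 are the only place where long persistence would be visible, and their denominator shrinks to subjects not yet re-treated. Because the rule changes after week 20, displayed response could rise from week 20 to week 24 while true response falls. A reader could take such a table as evidence of long-lasting effect.

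**Working it through.** **The plan's own figures.** The documents give no sample size, power or precision for duration. Their figures concern the week 4 rate, and they reproduce: 60% against 10% at 3:1, one-sided 0.025 and 90% power gives 42 + 14 = 56 with the continuity-corrected formula, and 1.96 × √(0.6 × 0.4/450) = 4.53%, the stated 4.5%. Neither bears on duration.

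**Effect of the exclusion rule.** Let r be the share of the arm still responding to the first treatment at a visit, and q the share re-treated earlier. A re-treated subject had FWS 2 or 3 from both raters (Protocol 7.3), so was not a responder when re-treated. All r responders are therefore among the 1-q not yet re-treated:

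- re-treated counted as non-responders: displayed rate = r
- re-treated excluded: displayed rate = r/(1-q)

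With assumed values:

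- r = 10%, q = 50%: 0.10/0.50 = 20%
- r = 10%, q = 80%: 0.10/0.20 = 50%
- r = 5%, q = 50%: 0.05/0.50 = 10%
- r = 5%, q = 90%: 0.05/0.10 = 50%

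**Effect of the change of rule after week 20.** The active arm of 525 was simulated under these assumptions: 60% respond at week 4; time to loss of response is lognormal with log-SD 0.4; an exponential lag follows until both raters score 2 or more; subjects are re-treated at the next eligible 4-weekly visit from week 12; nobody drops out.

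| Median time to loss (weeks) | Mean lag (weeks) | Week 20, SAP rule (non-responders) | Week 24, non-responder rule | Week 24, SAP rule (excluded) |
|---|---|---|---|---|
| 12 | 4 | 6.0% | 2.4% | 14.5% |
| 16 | 4 | 17.2% | 9.2% | 30.5% |
| 20 | 4 | 30.1% | 19.6% | 47.0% |
| 16 | 1 | 17.3% | 9.3% | 45.9% |
| 16 | 8 | 17.3% | 9.4% | 21.9% |

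In every row true response falls from week 20 to week 24 and displayed response rises. In the second row the implied q is 1 - 9.2/30.5 = 70%.

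**Can the data give a duration?** Yes. In cycle 1, FWS is recorded at weeks 1, 2, 4, 8 and 12 and then every 4 weeks until re-treatment (Protocol 10.1.1). With assumed medians of 12, 16 and 20 weeks and a mean lag of 4 weeks, the median read from the visit grid was 13.8, 17.9 and 22.1 weeks. The grid adds about 2 weeks, which interval-censored methods can address.

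**Do other planned tables fill the gap?** No. Exposure (SAP 8.5.1, 8.7.1) is last minus first administration plus 1 day. With one administration per cycle, this gives 1 day per cycle and not the cycle length.

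**How many subjects could a responder-only analysis use?** At the planning rates, 525 × 0.60 = 315 active and 175 × 0.10 = 17.5 placebo subjects.

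**The case against.** The sponsor can fairly say that duration is already operationalised. The proportion of treated subjects still responding at weeks 12, 16 and 20 against placebo is a randomised measure of persistence. Including subjects who never responded is the price of keeping that comparison. Weeks 16 and 20 treat re-treated subjects coherently, and the tables with the exclusion rule are labelled exploratory and descriptive. All of this stands, and it limits the point to the missing time-based estimate and the rule after week 20.

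Subjects not yet re-treated are also not all lasting responders. Some wait because the two raters disagree, others because of infection or inflammation at the injection site (Protocol 6.3.2). The selection is therefore imperfect, but its direction is not in doubt: r/(1-q) exceeds r whenever r and q are above zero.

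A reader might infer three stronger claims that the documents do not support:

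- **That every late summary drops re-treated subjects.** Week 12 is the earliest re-treatment visit, and weeks 16 and 20 keep re-treated subjects as non-responders.
- **That the trial cannot answer the duration question.** The 4-weekly data can, so the gap lies in the analysis plan and not in the design.
- **That an objective on duration after repeat treatment is left unanalysed.** Objective 2 covers a single treatment. The sentence "The duration of effect of BoNT/-DP after repeat treatment will be assessed in the open label extension study" is in the schedule rationale and has no matching endpoint. In the open-label cycles FWS is taken at week 4 and from week 12, week 8 is a telephone call, and follow-up ends between weeks 48 and 60.

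**Conclusion.** The point holds in limited form. Objective 2 has no definition of loss of effect and no estimate of duration as a time. Separately, the exploratory summaries after week 20 inflate displayed response by the factor 1/(1-q): 2-fold at q = 50% and 5-fold at q = 80%. The values of r and q, and the simulated distributions, are assumptions, since the documents give no re-treatment or duration distribution for this trial. The inflation itself needs only the re-treatment criterion and the exclusion rule. The primary endpoint, the hierarchy and the week 12, 16 and 20 comparisons are untouched. The change is worth making because it serves a stated objective from data already collected.

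**What to change.** 1. **SAP 8.6.3, visits after week 20 up to week 48.** Keep re-treated subjects in the FAS denominator and count them as non-responders, as at weeks 16 and 20, or show both versions. State how subjects missing without re-treatment are handled. The main week 16 and 20 analyses use observed values only.
2. **SAP 8.6.4, new exploratory analysis in all FAS subjects.** Estimate time from first treatment to the first visit from week 12 with FWS of 2 or more at maximum frown by both raters. Use an interval-censored or Kaplan-Meier method, by arm, with median, 95% CI and a site-stratified log-rank test. Describe it as time to relapse by both raters: a subject going from 2 to 0 to 1 has lost the composite response without having this event.
3. **SAP 8.6.4, descriptive companion.** Give time to loss of the composite response among week 4 responders, for the active arm only and without a between-arm test. With about 315 active and 17 or 18 placebo subjects, selected after randomisation, a comparison would be neither randomised nor informative.
4. **Open-label cycles, if covered at all.** Keep this descriptive, and state the coarse visit grid and the truncation at weeks 48 to 60.

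The cost is SAP wording, a few exploratory tables and figures, and less favourable late-visit rates. No new data are needed and no confirmatory result changes.
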